### **Comparing NGENUITY vs conventional microscope in a new Hydrus user**

**Design:** Prospective, masked study involving two new glaucoma Fellows learning to implant the Hydrus stent with supervision by single Attending. The fellows will alternate performing the surgeries (N=32) utilizing NGENUITY vs Zeiss Lumera conventional microscope.

**Hypothesis:** Hydrus cases using the NGENUITY will take less time, have fewer misdirected attempts, safer outcomes, and superior teaching value due to its better visualization of angle anatomy (higher resolution, improved depth of focus)

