#### **Key Endpoints:**

**Primary:** Total Hydrus time (time of cannula in /out), # of attempts (piercing TM)

**Secondary:** Other efficiency & efficacy endpoints: # of attempts entering reentering AC, # of times readjusting focus/microscope, rate of intraoperative adverse events, posture, and previously utilized Fellow and Attending questionnaire

**Exploratory:** Safety outcomes at POD#1 and POM#1

**Statistical Considerations:** N= 32, descriptive qualitative stats

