#### **Inclusion Criteria:**

- Patients with mild to moderate primary open angle glaucoma as defined by AGS with visually significant cataract undergoing uncomplicated cataract surgery and Hydrus microstent
- Patient is amenable to being a Fellow's case
- Either eye or both eyes may participate

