#### **Exclusion Criteria:**

- Lack of patient cooperation severely affecting ability to place stent with any visualization technique
- Angle abnormalities including PAS in nasal quadrant
- Unable to properly visualize the angle due to complicated cataract surgery

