Comparing NGENUITY vs Conventional Microscope in a New Hydrus User

Statistical Analysis Plan

NCT05529966

March 14, 2025

The original planned sample size for this study was 32 participants, with each participant enrolling a single study eye. However, it was later determined that if both eyes of a participant were eligible for the study, the same participant could be enrolled for their second eye surgery, resulting in a revised planned sample size of a total of 32 eyes. Additionally, the study protocol was modified to include a total of three glaucoma fellows participating in the surgeries, rather than the originally planned two. To analyze the outcome measures, a two-tailed t-test with two-sample unequal variance was used for primary and secondary outcomes with both NGENUITY and convention microscope groups. After Bonferroni correction, the new threshold for statistical significance was <0.002083333.

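### No randomisation or allocation concealment is described; the only rule is an ambiguous alternation, so eligibility and exclusions can be judged with the microscope already known

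*Protocol*

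**What the plan says.** The protocol's Design paragraph describes the study as "Prospective, masked study involving two new glaucoma Fellows learning to implant the Hydrus stent with supervision by single Attending", and then gives its one sentence on assignment: "The fellows will alternate performing the surgeries (N=32) utilizing NGENUITY vs Zeiss Lumera conventional microscope". It does not say who is masked.

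Under Inclusion Criteria, one condition is "Patient is amenable to being a Fellow's case"; one eye or both may enter. Under Exclusion Criteria, two of the three items can be judged around or during surgery: "Lack of patient cooperation severely affecting ability to place stent with any visualization technique" and "Unable to properly visualize the angle due to complicated cataract surgery".

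The primary endpoints (Key Endpoints) are the time the Hydrus cannula is in the eye and the number of attempts at piercing the trabecular meshwork.

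The SAP raises the number of fellows from two to three and lets a participant's second eye enter, "resulting in a revised planned sample size of a total of 32 eyes". It adds nothing about how a microscope is assigned, including for second eyes. Its analysis of primary and secondary outcomes is a two-sided, unequal-variance t-test between microscope groups, with no covariate and a Bonferroni threshold of 0.002083333.

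**The concern.** A comparison of two devices needs either an assignment that nobody entering patients can foresee, or an analysis and conclusion that allow for its absence. Here the assignment can be foreseen or chosen, and several judgements about whether an eye counts can be made afterwards.

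Both primary endpoints plausibly depend on how difficult the eye is (an inference; the documents do not discuss it). If difficult eyes were more often deferred, left out or excluded under one microscope, the other would look slower and need more attempts without being worse. Such a difference has a consistent direction, unlike chance imbalance, so it does not shrink as eyes are added. Adjusting for fellow or case order would not remove it either, because the selection is on the eye.

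**Working it through.** **1. The two readings of the assignment sentence.** Grammatically, the fellows alternate; no microscope sequence is written out.

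- *The microscope alternates by case.* Anyone who knows the last case can name the next device: 32 of 32 if the starting device is known, or (31 + 0.5)/32 = 98.4% if the first has to be guessed.
- *Only the fellows alternate.* The microscope rule is then unstated. No predictability figure follows, but nothing prevents free choice.

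Neither reading gives concealment. For comparison, concealed simple 1:1 randomisation allows 50% correct guesses. Permuted blocks whose size is known to the team allow 75% (size 2), 71% (size 4) or 67% (size 8). For size 4, the chances of a correct guess at positions 1 to 4 are 1/2, 2/3, 2/3 and 1, so (0.5 + 0.667 + 0.667 + 1)/4 = 0.708. Varying, undisclosed sizes make guessing harder than a known size does; that was not computed.

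**2. What can be decided with the device known.** No rule requires consecutive enrolment or that enrolment precede assignment. The cooperation exclusion is a judgement. The visualisation exclusion depends on how the cataract surgery went, so it can arise after the microscope is in use. Masking does not close the gap: the operating fellow and the Attending can see which microscope they are using, and masking an outcome assessor is different from concealing the next assignment at enrolment.

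**3. Whether the planned test protects against it.** The SAP threshold reproduces as 0.05/24 = 0.00208333; the count of 24 tests is inferred, not stated. The sample size of 32 cannot be reproduced, because no effect size, SD or power is given.

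Assume 16 eyes per microscope, independent eyes, equal variances, no true device effect, and a case-mix shift of *b* SD between arms. With equal arms, the unequal-variance and pooled t statistics coincide, so the pooled form with 30 degrees of freedom is a fair approximation. The noncentrality is δ = *b* × √(16/2) = 2.828*b*. The rejection rate is 1 − F(t\*; 30, δ) + F(−t\*; 30, δ), where F is the noncentral t distribution function and t\* is the two-sided critical value: 2.042 at 0.05 and 3.370 at 0.002083.

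| Assumed shift *b* (SD) | δ | False positives at 0.05 | At 0.002083 | Multiple of 0.002083 |
|---|---|---|---|---|
| 0 | 0 | 5.0% | 0.21% | 1 |
| 0.25 | 0.707 | 10.5% | 0.8% | about 4 |
| 0.5 | 1.414 | 27.8% | 3.8% | about 18 |
| 1.0 | 2.828 | 78.1% | 31.9% | about 153 |

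The Bonferroni threshold makes false positives rarer in absolute terms but does not restore the nominal rate. At every *b* the estimated difference is off by the full *b* SD, whatever the p-value.

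**The case against.** The strongest reply has four parts.

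- **The text does not say that microscopes alternate.** This stands. The near-certain predictability holds only on that reading. On the other, the defect is an unspecified assignment method, which is no safer.
- **A reader might infer that the team, or the Attending, chooses which patients become Fellow cases and steers easy eyes to one device.** The documents do not support that. The inclusion criterion concerns the patient's willingness, and nothing says who books cases or in what order. What the text does support is that nothing prevents selection, and that two exclusions leave room for judgement.
- **The harm is unquantified, and the threshold is strict.** The first part stands: every shift in the table is assumed. With 32 eyes, chance imbalance in difficulty is also expected under proper randomisation, so an imbalance alone would not prove selection. Randomisation removes the systematic direction, which the test cannot recognise.
- **The study may be finished, and neither document calls it randomised.** The SAP is dated March 2025 and describes the analysis in the past tense, so a new list may help few or no eyes. There is no claim of randomisation to retract. But neither document says that the comparison is non-randomised, and the hypothesis attributes better performance to the microscope.

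**Conclusion.** The concern holds in a limited form. No randomisation or concealment is described, and on either reading of the alternation sentence the device can be known or chosen before an eye is entered or excluded. Selection on eye difficulty could bias both primary endpoints in a consistent direction, and the planned unadjusted test would not remove it. The size and direction of any bias are unknown. The error rates above are conditional on assumed shifts of 0.25 to 1.0 SD, equal arms and independent eyes.

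Two stronger conclusions may tempt a reader. One is that the results are biased in favour of NGENUITY: the stated hypothesis favours that device, but no document shows that cases were steered. The other is that fellow and microscope are completely confounded. That would follow if two fellows and two microscopes both alternated strictly case by case (each fellow doing 16 eyes on one device), but the documents do not state such a lockstep. With the current three fellows, strict alternation of both would give 5 or 6 eyes in each fellow-by-device cell.

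**What to change.** **Eyes not yet operated on.** Assign the microscope from a concealed random list in blocks of varying, undisclosed size within each fellow. Reveal the next entry only after the eye is confirmed eligible and booked. Because the visualisation exclusion can still arise during surgery, report every exclusion made after assignment, by device and with its reason. State in the protocol who is masked and how a second eye receives its microscope.

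**Eyes already operated on.** State in the SAP and report how each microscope was actually assigned. Tabulate eye difficulty and exclusions by device, describe the comparison as non-randomised, and limit the conclusion to an association between microscope and outcome. Given the SAP's past tense, this is probably the part that applies.

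**Cost.** A prepared list, a few lines of protocol text and one or two tables, with no extra patients or visits. The microscope is known later, so room set-up needs slightly more flexibility, and the conclusion is weaker for eyes already done.

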#### **Key Endpoints:**

**Primary:** Total Hydrus time (time of cannula in /out), # of attempts (piercing TM)

**Secondary:** Other efficiency & efficacy endpoints: # of attempts entering reentering AC, # of times readjusting focus/microscope, rate of intraoperative adverse events, posture, and previously utilized Fellow and Attending questionnaire

**Exploratory:** Safety outcomes at POD#1 and POM#1

**Statistical Considerations:** N= 32, descriptive qualitative stats

#### **Inclusion Criteria:**

- Patients with mild to moderate primary open angle glaucoma as defined by AGS with visually significant cataract undergoing uncomplicated cataract surgery and Hydrus microstent
- Patient is amenable to being a Fellow's case
- Either eye or both eyes may participate

#### **Exclusion Criteria:**

- Lack of patient cooperation severely affecting ability to place stent with any visualization technique
- Angle abnormalities including PAS in nasal quadrant
- Unable to properly visualize the angle due to complicated cataract surgery

Comparing NGENUITY vs Conventional Microscope in a New Hydrus User

Statistical Analysis Plan

NCT05529966

March 14, 2025

The original planned sample size for this study was 32 participants, with each participant enrolling a single study eye. However, it was later determined that if both eyes of a participant were eligible for the study, the same participant could be enrolled for their second eye surgery, resulting in a revised planned sample size of a total of 32 eyes. Additionally, the study protocol was modified to include a total of three glaucoma fellows participating in the surgeries, rather than the originally planned two. To analyze the outcome measures, a two-tailed t-test with two-sample unequal variance was used for primary and secondary outcomes with both NGENUITY and convention microscope groups. After Bonferroni correction, the new threshold for statistical significance was <0.002083333.

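### Both eyes of one participant may count toward the 32, but the only test named is an unpaired t-test that treats every eye as independent

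*SAP*

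**What the plan says.** The SAP is a single paragraph. It describes the starting position: "The original planned sample size for this study was 32 participants, with each participant enrolling a single study eye". It then changes the unit: "the same participant could be enrolled for their second eye surgery, resulting in a revised planned sample size of a total of 32 eyes". The Protocol agrees under Inclusion Criteria: "Either eye or both eyes may participate".

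On allocation, the Protocol's Design statement says only "The fellows will alternate performing the surgeries (N=32) utilizing NGENUITY vs Zeiss Lumera conventional microscope". It gives no arm ratio and no rule linking a participant's second eye to the microscope used for the first.

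The primary endpoints under Key Endpoints are "Total Hydrus time (time of cannula in /out), # of attempts (piercing TM)". The Protocol's statistical entry is descriptive only. The SAP names one test for the primary and secondary outcomes, "a two-tailed t-test with two-sample unequal variance was used for primary and secondary outcomes with both NGENUITY and convention microscope groups", and one threshold: "After Bonferroni correction, the new threshold for statistical significance was <0.002083333". Neither document mentions pairing, clustering, a mixed model, GEE, robust standard errors or a one-eye sensitivity analysis.

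**The concern.** With one eye per participant, between-eye dependence could not arise. The change to eyes removed that safeguard, and the analysis was not adapted. The Welch test allows for unequal variances between arms, but it still assumes that all 32 observations are independent.

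Two eyes of one patient share that patient's anatomy and cooperation. The Protocol's Exclusion Criteria themselves recognise that cooperation can affect stent placement. Some positive correlation is therefore plausible, though its size is not given.

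The direction of the error depends on allocation. Pairs on the same microscope carry less information than the test credits, so false positives rise. Pairs split across microscopes carry more, so the test gives up precision that a paired analysis would use. From the documents, a reader cannot tell whether p-values set against 0.002083 are too small, too large or about right. The Bonferroni step does not help, because it addresses the number of tests and not the dependence between eyes.

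**Working it through.** **Inputs from the documents.** 32 eyes with second eyes allowed (SAP; Protocol, Inclusion Criteria). Two-sided unpaired Welch test and threshold 0.002083333 (SAP). Alternation across surgeries (Protocol, Design).

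**Assumed, because not given.** 16 eyes per arm; the number of bilateral participants; the between-eye correlation rho; S same-microscope pairs and O split pairs; a normal outcome.

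**Step 1: the plan's own figures.** 0.05/24 = 0.0020833, which matches the threshold, although neither 0.05 nor 24 is stated. N = 32 cannot be reproduced, because no effect size, SD or power is given.

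**Step 2: variance.** With independent eyes and 16 per arm, the variance of the difference in means is 2σ²/16 = σ²/8. Each same-microscope pair adds 2·rho·σ²/16², and each split pair subtracts the same amount. Hence

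true variance / assumed variance = 1 + rho × (S − O)/16.

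For 8 bilateral participants (24 participants in all) and rho = 0.5:
- all split: 1 + 0.5 × (−8)/16 = 0.75
- 4 same, 4 split: 1 + 0 = 1.00
- all same: 1 + 0.5 × 8/16 = 1.25, or an effective 32/1.25 = 25.6 eyes

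**Step 3: type I error of the Welch test.** Simulated with 400,000 replicates per cell; 8 bilateral participants, rho = 0.5:

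| Same / split pairs | At nominal 0.05 | At nominal 0.00208 |
|---|---|---|
| 0 / 8 | 0.025 | 0.0004 |
| 2 / 6 | 0.037 | 0.0010 |
| 4 / 4 | 0.050 | 0.0020 |
| 6 / 2 | 0.065 | 0.0033 |
| 8 / 0 | 0.080 | 0.0054 |

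A separate run with 200,000 replicates gave 0.025 (0.0005) for all split and 0.080 (0.0056) for all same. The relative distortion is larger at the stricter threshold. For all same it is 0.080/0.05 = 1.6-fold against 0.0054/0.00208 = 2.6-fold.

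**Step 4: other assumptions.**
- 8 bilateral, rho = 0.1, all split to all same: 0.044 to 0.055 (0.0015 to 0.0027 at nominal 0.00208).
- 8 bilateral, rho = 0.3, all split to all same: 0.034 to 0.067 (0.0009 to 0.0038).
- 4 bilateral, rho = 0.3: 0.041 all split, 0.049 with 2/2, 0.058 all same.
- Outer limit, all 16 participants bilateral, rho = 0.5: 0.008 all split, 0.051 with 8/8, 0.112 all same.
- No bilateral participants, or rho = 0: no error.

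**Step 5: do the alternatives behave at this size?** A mixed model with a participant random intercept and Kenward-Roger degrees of freedom (4 or 8 bilateral participants, rho 0 or 0.5) gave type I error of 0.035 to 0.059 at nominal 0.05 and 0.0005 to 0.0027 at nominal 0.00208.

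A participant-level permutation test (8 bilateral, rho = 0.5; 10,000 replicates, 6,000 permutations) was checked at nominal 0.05 only:

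| Outcome and test | All split | 4/4 | All same |
|---|---|---|---|
| Normal, permutation | 0.045 | 0.053 | 0.047 |
| Count (1 + Poisson 0.8), permutation | 0.028 | 0.029 | 0.031 |
| Same count, Welch | 0.027 | 0.049 | 0.072 |

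The permutation test is conservative for tied counts, but its level does not depend on how the pairs fell. GEE with a small-sample correction was not simulated.

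**The case against.** The strongest reply is that no harm is established. The SAP permits second eyes, but neither document says that any were enrolled. The correlation is also unknown. The primary outcomes are cannula time and attempts at separate operations by learners, so rho may be low, and at rho = 0.1 the error with 8 bilateral participants is small.

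The extremes may also be improbable. If a second eye is equally likely to get either microscope, the number of same-microscope pairs among 8 is Binomial(8, 0.5). All same and all split then each have probability 1/256 = 0.4%, and 2 to 6 same has 238/256 = 93%. Averaged over that distribution, Welch type I error is about 0.050 at nominal 0.05 and 0.0021 at nominal 0.00208. On this view, disclosure and one sensitivity analysis would be enough until the counts are known.

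Much of this stands as a limit on size. It does not remove the gap. Equal chance for the second eye is itself an assumption, since the alternation rule does not settle it. A test that is right on average over allocations can still be off for the one that occurred: 0.037 to 0.065 for 2 to 6 same-microscope pairs at rho = 0.5. Split pairs also lose precision under any unpaired test. The numbers bilateral and their allocation may be reported elsewhere; the two documents do not give them.

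**Conclusion.** The concern holds. The plan admits correlated observations and names only a test that assumes none. Standard errors are wrong whenever correlated bilateral pairs are present and same-microscope and split pairs do not balance.

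Confidence is high on the omission. No claim is made about the direction or size of any effect on the results. The illustrated range of 0.025 to 0.080 at nominal 0.05 rests on 16 eyes per arm, 8 bilateral participants, rho = 0.5 and normal data, and it shrinks to nothing if no participant was bilateral. It should be fixed because the remedy is cheap and the pair counts settle whether it matters.

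**What to change.** 1. Report the number of participants, the number bilateral, and how many pairs were same-microscope or split. If none were bilateral, the point closes.
2. For Hydrus time and other continuous outcomes, replace the Welch test with a linear model that has a participant random intercept (REML, Kenward-Roger degrees of freedom).
3. For attempt counts and adverse-event rates, use GEE clustered on participant with a suitable link and a small-sample correction. If events are too few, use a participant-level permutation test that moves same-microscope pairs together, flips labels within split pairs and permutes single eyes among themselves. State explicitly which method applies to posture and the questionnaires.
4. Add a first-eye-only sensitivity analysis.
5. The SAP describes the analysis in the past tense, so label any reanalysis as post hoc.

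**Cost.** SAP wording and a modest reanalysis, provided that a participant identifier is held for each eye, which is not stated. The participant variance will be imprecise if few participants are bilateral. With 8 bilateral participants, first-eye-only analysis uses 24 eyes, so the SE widens by sqrt(32/24) = 1.155, about 15%, if pairs balance or rho = 0. Against the true 32-eye SE at rho = 0.5, the widening is 1.155/sqrt(1.25) = 1.03 (all same) to 1.155/sqrt(0.75) = 1.33 (all split). P-values may become less favourable. This deals with pairing only; differences between the three fellows are a separate matter.

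### The only comparative test ignores operating fellow and case order, and the allocation of microscopes within fellow is not stated

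*SAP*

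**What the plan says.** The protocol's statistical section is a single line, "N= 32, descriptive qualitative stats", and names no test, model or covariate. The SAP, which is one paragraph, supplies the only comparative method: "a two-tailed t-test with two-sample unequal variance was used for primary and secondary outcomes with both NGENUITY and convention microscope groups". It adds a significance level: "After Bonferroni correction, the new threshold for statistical significance was <0.002083333".

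The protocol's Design paragraph describes the operators as "two new glaucoma Fellows learning to implant the Hydrus stent with supervision by single Attending". On allocation it says only: "The fellows will alternate performing the surgeries (N=32) utilizing NGENUITY vs Zeiss Lumera conventional microscope". The SAP later reports that "the study protocol was modified to include a total of three glaucoma fellows participating in the surgeries". It does not say when the third fellow joined or how that fellow's cases were assigned.

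Under Key Endpoints, the two primary outcomes are the time the cannula is in the eye and the number of attempts at piercing the trabecular meshwork. Neither document contains a term, stratum, block or sensitivity analysis for operating fellow or for case order.

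**The concern.** Both primary endpoints plausibly depend on who is operating and how many cases that person has already done. A two-group t-test treats all 32 operations as exchangeable apart from the microscope. What that costs depends on how microscopes were spread over each fellow's cases.

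- **Roughly balanced within fellow:** skill and learning affect both arms alike, so the difference is close to unbiased. The variation they cause still enters the t-test's standard error, which is then too large for the comparison made. The test becomes conservative and loses power.
- **Unbalanced within fellow:** part of the difference between fellows, or between early and late cases, is counted as a microscope effect.

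The alternation sentence in the Design paragraph concerns the fellows. Its bearing on the microscopes is ambiguous, and it was written for two fellows.

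**Working it through.** **The plan's own figure.** The SAP threshold equals 0.05/24 = 0.00208333. The 0.05 and the 24 are inferred, since neither is stated (0.025/12 gives the same value). N = 32 cannot be reproduced because no effect size, SD or power is given.

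**Inputs.** From the documents: 32 eyes, three fellows, a two-sided unequal-variance t-test and the threshold above. Assumed, because the documents give no values: 11/11/10 cases per fellow, residual SD 1, microscope effect 1 SD, a learning component L that decays by a factor exp(-0.25) per case, and between-fellow SD F. The adjusted model is

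outcome = microscope + fellow (two indicators) + log(case number within fellow),

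with 32 - 5 = 27 residual degrees of freedom.

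**Step 1: precision when allocation does not favour either microscope.** Simulated power at 0.002083, 40,000 trials per scenario:

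| Assumed L, F | Paired within fellow: t-test / adjusted | Random 16/16: t-test / adjusted |
|---|---|---|
| 0, 0 | 31.6% / 31.0% | 31.2% / 26.6% |
| 0.5, 0.25 | 27.9% / 30.6% | 28.9% / 27.2% |
| 1, 0.5 | 20.6% / 30.6% | 22.3% / 26.5% |

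With pairing, adjustment gains 10.0 points at the largest assumed effects and costs 0.6 when there are none. With random allocation it gains 4.2 points at the largest effects and loses 4.6 and 1.7 points in the other two scenarios.

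**Step 2: bias under hypothetical layouts.** Suppose one fellow differs from the others by a gap G and each arm has 16 cases. The bias is then

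G x (that fellow's NGENUITY cases/16 - that fellow's conventional cases/16).

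Take G = 1 SD, no learning and no true microscope effect. The nominal type I error is 0.21%.

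| Layout (NGENUITY/conventional by fellow) | Bias | t-test type I error |
|---|---|---|
| Three fellows rotating from the start, microscopes alternating case by case (6/5, 5/6, 5/5) | 6/16 - 5/16 = 0.06 SD | 0.09% |
| NGENUITY cases 8, 5 and 3 by fellow | 8/16 - 3/16 = 0.31 SD | 0.53% |
| Third fellow joins the rotation after operation 16 (11/3, 2/11, 3/2) | 11/16 - 3/16 = 0.50 SD | 2.0% |
| Third fellow does every case after operation 16 (8/0, 0/8, 8/8) | 8/16 - 0/16 = 0.50 SD | 2.4% |

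The third row depends on where the rotation restarts. With splits 11/2, 3/11, 2/3 the bias is 9/16 = 0.56 SD and the error is 3.2%.

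**Step 3: what adjustment costs when fellow and microscope overlap.** The unadjusted variance factor is 1/16 + 1/16 = 0.125. The adjusted factor is 0.1262 for the three-fellow rotation, 0.1922 when the third fellow joins the rotation late, and 0.2526 when the third fellow does all later cases. The last two give standard errors sqrt(0.1922/0.125) = 1.24 and sqrt(0.2526/0.125) = 1.42 times the balanced one, and adjusted power of 16% and 10%.

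**Step 4: number of attempts.** With outcomes simulated as 1 + Poisson under random allocation, a quasi-Poisson model with the same covariates rejected 0.16% to 0.41% of null trials at the 0.2083% level. In a separate check of five settings, the t-test rejected 0.08% to 0.19% and quasi-Poisson 0.23% to 0.35%. The count model is mildly liberal at this threshold, and no power advantage was shown for it.

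**The case against.** The strongest reply is that no bias has been shown. The alternation sentence can equally mean that each fellow alternates between microscopes, which would give near-even splits and almost no bias. The uneven layouts above are hypothetical, and neither document says that any of them occurred. This stands: on bias, the documents support a request for disclosure and not a finding of error.

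A reader might infer that fellows and microscopes alternated in lockstep, so that each fellow used only one microscope. Over 32 cases with two fellows that gives 16/0 and 0/16, a bias equal to the whole fellow gap, a type I error of 31% for a 1 SD gap, and a model that cannot be estimated (rank 3 of 4). The documents do not support this as a description of the trial. It requires two fellows to do all the operations, whereas the SAP reports three. It describes a superseded design and serves only as an illustration.

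A second reply is that adjustment can cost power, as the random-allocation column shows. That also stands. The learning and fellow effects are assumed, so the documents cannot settle whether precision improves. A third is that replacing the t-test for number of attempts is not justified. Step 4 bears this out, and the remedy is limited accordingly.

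Finally, the SAP is in the past tense, so results may already be known. This limits the status an added model can claim, but not the value of reporting it.

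**Conclusion.** The omission is plain in the text: microscope is the only factor in the only comparative test, the operators are learners, and allocation within fellow is unstated. The consequence is conditional. With rough balance within fellow, the t-test is not materially biased and the loss is one of precision. For a 1 SD effect at 0.002083, power is about 21% against 31% adjusted, under pairing with L = 1 and F = 0.5, and there is no useful gain if those effects are absent. With imbalance, the estimate also contains a share of the differences between fellows, for example 0.31 to 0.50 SD per 1 SD gap in the uneven layouts tabulated. All of these sizes rest on assumed values.

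A reader might go further and conclude that the microscope comparison is confounded, or that adjustment is bound to raise power. The documents support neither conclusion. The change should be made. Confidence is medium, because the actual allocation is unknown. Enrolment of both eyes of a participant is a separate matter that these terms do not address.

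**What to change.** 1. State how microscopes and the third fellow's cases were assigned, and tabulate cases by fellow, microscope and case number within fellow.
2. Analyse Hydrus time with a linear model containing microscope, fellow as a fixed effect, and case order within fellow (log case number, or another named form). Report the adjusted difference with its confidence interval.
3. If t-test results have already been seen, keep the t-test and show the adjusted model beside it, labelled as a post hoc sensitivity analysis.
4. For number of attempts, keep the unequal-variance t-test. Add an analysis adjusted for fellow and case order (linear or count model) as a sensitivity analysis only.
5. If a fellow used only one microscope, say that this fellow's cases add no within-fellow comparison.

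The cost is three degrees of freedom. If fellow and learning effects are absent, power at 0.002083 falls by under 1 point with pairing (31.6% to 31.0%) and by about 4 to 5 points under random allocation (31.2% to 26.6%). It falls further if fellow and microscope partly overlap. Fellow and case order must be retrievable for every operation, which the documents do not confirm. Case number within the study measures experience only if fellows did no such cases elsewhere. The fix covers the primary endpoints and does not specify models for the secondary ones.
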